2.2. Treatment Phase

Study Schedule Protocol H8H-MC-LAHB: Treatment Phase

Procedure	Treatment Phase: Periods 1-5				Follow-up Phase	Comment
Study Day	-1	1	2	D/C or ET	20	Minimum of 3 days = 72 h washout between doses
Visits	I	I	I		O	I: inpatient; O: outpatient; Follow-up = approximately 1 week after last dose of study drug.
Weight	X			X	X	Weight will be collected at Treatment Phase Period 1, D/C or ET, and Follow-up.
ECG	X	0, 2, 4	24	X	X	
Study Drug Dosing		X				Study drug will be administered on Day 1 after an overnight fast.
AE/Medication Review	X	X	X	X	X	
PE	X					Full PE at first CRU admission. Symptom-driven PE at all other time points as deemed necessary by PI.
BP/Pulse	X	0, 1, 2, 4, 6	24	X	X	Single supine BP and pulse rate. Follow same window as PK.
Urine Drug Screen and Alcohol Screen	X				X	Urine Drug and Alcohol screen will be collected at Treatment Phase Period 1 and Follow-up (additional test will be performed at Periods 2-5 if subject discharged between periods).
Pregnancy Test	X				X	Pregnancy test will be collected at Treatment Phase Period 1 only and Follow-up (additional test will be performed at Periods 2-5 if subject discharged between periods).
CBC and Chemistry	X				X	Fasting samples on Days -1 of all periods.
VAS training	X					VAS training to occur on Day -1 of each Period
Drug Effects Battery		0, 0.25, 0.5, 1, 1.5, 2, 2.5, 3, 3.5, 4, 4.5, 5, 6, 8, 12	24			Overall Drug Liking and Take Drug Again assessed at 12 and 24 hours postdose only.
Drug Similarity VAS Battery			24			
C-SSRS/ Self-Harm	X			X	X	A self-harm form may be administered at time of C-SSRS. C-SSRS/Self Harm will be administered on Day -1 Treatment Phase Period 1, D/C or ET, and Follow-up (additional test will be performed at Periods 2-5 if subject discharged between periods).
PK		0, 0.5, 1, 1.5, 2, 2.5, 3, 4, 6, 8, 12	24			
Genetic Sample	X					Genetic samples will be collected at the first period of Treatment Phase only.

Abbreviations: AE = adverse event; BP = blood pressure; CBC = complete blood counts; CRU = clinical research unit; C-SSRS = Columbia-Suicide Severity Rating Scale; D/C = discontinuation; ECG = electrocardiogram; ET = early termination; h = hour; PE = physical examination; PI = principle investigator; PK = pharmacokinetics; VAS = visual analogue scale.

Note: if multiple procedures take place at the same time point, the following order of the procedure should be used: ECG, vital signs, and venipuncture.

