3.3. Benefit–Risk Assessment

This study compares the abuse potential for lasmiditan versus placebo, and versus alprazolam in experienced recreational polydrug users. Thus, there is no anticipated therapeutic benefit for the subjects in this study.

To date, lasmiditan has been tolerated by healthy subjects after single dose oral administration up to 400 mg. The most frequently reported AEs in clinical studies include somnolence, dizziness, fatigue, and hot flash. More information about the known and expected benefits, risks, SAEs, and reasonably anticipated AEs of lasmiditan are to be found in the Investigator's Brochure (IB).

Alprazolam, a short-acting benzodiazepine, has been chosen as a positive control. Potential risks from alprazolam include sedation and somnolence. Administration of lasmiditan and alprazolam will be conducted in inpatient setting, with monitoring of adverse reactions, vital signs, and electrocardiograms (ECGs). Adverse events will be managed with supportive care.

Only subjects with a prior history of recreational drug use will be enrolled in this study and a maximum of 2 doses within the therapeutic dose range of alprazolam will be administered to minimize potential risks, including the risk for dependence. Subjects at risk of adverse reaction from alprazolam, including subjects with a prior history of benzodiazepine dependence, seizures, or depression and concomitant use of CYP3A inhibitors will be excluded from the study.

Information about known risks for alprazolam can be found in the package insert for alprazolam.

4. Objectives and Endpoints

Table LAHB.1 shows the objectives and endpoints of the study.

Table LAHB.1. Objectives and Endpoints

Objectives	Endpoints
Primary To assess the abuse potential of lasmiditan compared to the positive control alprazolam and placebo	The difference in the maximal effect score (E_{max}) during the 24 hours after dosing of the at-the-moment 100-mm bipolar Drug Liking Visual Analog Scale (VAS) scores for: 
 • alprazolam versus placebo • lasmiditan versus alprazolam • lasmiditan versus placebo

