5.1. Overall Design

This study is a Phase 1, randomized, subject- and investigator-blind, placebo- and active-controlled, crossover clinical trial in adult subjects who are recreational poly-drug users. This study includes 4 phases:

Screening Phase: Subjects will sign informed consent before their entry to the study and completion of all screening procedures. Screening visits should be within 28 days of dosing in Qualification Phase. Subjects who fail screening may not be rescreened.

Qualification Phase: Eligible subjects who meet all inclusion criteria and none of the exclusion criteria will enter a subject- and investigator-blind placebo-controlled, 2-period crossover design Qualification Phase. Subjects will be randomized to a test dose of 1-mg alprazolam and placebo in a crossover manner with a washout period of at least 3 days (72 hours) between each dose. “Drug-liking” response will be assessed before and after alprazolam and placebo administration using a 100-mm bipolar Drug Liking Visual Analog Scale (VAS). Only subjects who meet alprazolam qualification criteria (see Section 6.1.1) will be eligible to enter the Treatment Phase.

Treatment Phase: This will be a subject- and investigator-blind, placebo- and active-controlled, 5-period crossover design. Subjects will be randomized to 1 of 10 dosing sequences; each dosing sequence consists of 5 dosing periods that evaluate the abuse potential of 1 of the 5 study treatments: placebo, 2-mg alprazolam, and 100-mg lasmiditan, 200-mg lasmiditan, and 400-mg lasmiditan. The washout period between each dose should be at least 3 days (72 hours).

Eligible subjects will be admitted to the clinical research unit (CRU) on Day -1 before the planned study drug dosing during each of the dosing periods in both the Qualification Phase and Treatment Phase. After verification of subjects’ eligibility, including a urine drug screen at time of CRU admission, blinded study drug will be administered on Day 1 after an overnight fast. Abuse potential will be assessed using Drug Effects VAS Battery. Adverse events, vital signs, and ECGs will be monitored, and PK samples will be collected according to the Study Schedule (Section 2).

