10.3.3. Abuse Potential Analyses

Descriptive statistics for the Drug Liking VAS will be reported for each treatment and for each paired difference among treatments. A linear mixed-effects model, which includes period, sequence, and treatment as fixed effects, and subject as a random effect will be used to evaluate the hypothesis tests of primary interest at the peak of drug response effects (E_{max}) at a significance level of 0.05 (1-sided). The following pairwise comparisons will be made:

- alprazolam minus placebo, with null hypothesis that the difference is ≤ 15 mm;
- alprazolam minus each dose of lasmiditan, with the null hypothesis that the difference is ≤ 5 mm; and

- each dose of lasmiditan minus placebo, with the null hypothesis that the difference is ≥ 14 mm.

Least square mean estimates and 90% confidence intervals will be reported for each treatment and for each paired difference among treatments.

The residuals from the mixed-effect model will be investigated for normality using the Q-Q plot. If this normality assumption is not met, paired sample t-test or nonparametric test will be considered based on actual data distributions. For nonparametric analyses, pairwise treatment comparisons will be assessed using the Wilcoxon signed-rank test on the within-subject differences, and median and intraquartile range will be reported.

Descriptive statistics for each other element of the Drug Effects VAS Battery, aside from Drug Liking VAS, and for time to peak effect will be reported for each treatment. If the normality assumptions of mixed-effects model on the residuals are met, a linear mixed-effects model, which includes period, sequence, and treatment as fixed effects, and subject as a random effect will be used to provide least square mean estimates and 90% confidence intervals for each treatment. The residuals from the mixed-effect model will be investigated for normality using the Q-Q plot. If the normality assumptions of mixed-effects model are not met, alternative approaches such as paired t-test or non-parametric test may be considered based on the actual data distributions. For non-parametric analyses, the median and intra-quartile range will be reported for each treatment.

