3. INTRODUCTION

This SAP has been developed after review of the Clinical Study Protocol (final version dated 24 July 2017 and Protocol Amendment (c) (final version dated 06 September 2017).

This SAP describes the planned analysis of the safety, tolerability, pharmacokinetic (PK) and pharmacodynamic (PD) data from this study. A detailed description of the planned TFLs to be presented in the clinical study report (CSR) is provided in the accompanying TFL shell document.

The intent of this document is to provide guidance for the statistical and PK analyses of data. In general, the analyses are based on information from the protocol, unless they have been modified by agreement between Eli Lilly and Company and Covance Early Clinical (EC) Biometrics. A limited amount of information concerning this study (e.g., objectives, study design) is given to help the reader's interpretation. This SAP must be signed off prior to first subject administration for this study. When the SAP and TFL shells are agreed upon and finalized, they will serve as the template for this study's CSR.

This SAP supersedes the statistical considerations identified in the protocol; where considerations are substantially different, they will be so identified. If additional analyses are required to supplement the planned analyses described in this SAP, they may be performed and will be identified in the CSR. Any substantial deviations from this SAP will be agreed upon between Eli Lilly and Company and Covance EC Biometrics and identified in the CSR. Any minor deviations from the TFLs may not be documented in the CSR.

This SAP is written with consideration of the recommendations outlined in the International Conference on Harmonisation (ICH) E9 Guideline entitled Guidance for Industry: Statistical Principles for Clinical Trials¹ and the ICH E3 Guideline entitled Guidance for Industry: Structure and Content of Clinical Study Reports².

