9.4.2 Pharmacodynamic Statistical Methodology

Descriptive statistics for the Drug Liking VAS will be reported for each treatment and for each paired difference among treatments.

The E_{max} will be derived as the maximum at-the-moment Drug Liking VAS score among all the individual values that are collected at the scheduled assessment timepoints. The time to E_{max} is the corresponding timepoint at which the maximum score occurs. These will be derived for both the Qualification Phase and Treatment Phase separately for each treatment.

A linear mixed-effects model, which includes period, sequence, and treatment as fixed effects, and subject as a random effect will be used to evaluate the hypothesis tests of primary interest at the E_{max} at a significance level of 0.05 (1-sided). The following pairwise comparisons will be made:

- Alprazolam minus placebo, with null hypothesis that the difference is ≤ 15 mm;

- Alprazolam minus each dose of lasmiditan, with the null hypothesis that the difference is ≤ 5 mm; and
- each dose of lasmiditan minus placebo, with the null hypothesis that the difference is ≥ 14 mm.

Least square mean estimates and 90% confidence intervals (CI) will be reported for each treatment and for each paired difference among treatments.

An example of the SAS code that will be used is as follows:

```
proc mixed data=xxxx;
class trtmnt period sequence subject;
model emax = trtmnt period sequence / ddfm=kr alpha=0.1 residual outp=pred;
random subject;
lsmeans trtmnt / pdiff=control alpha=0.1; /*Produce 90% CI*/
lsmeans trtmnt / pdiff=controll alpha=0.05; /*Test at 0.05 significance 1-sided*/
ods output lsmeans=lsml1;
ods output diffs=diff1;
run;

/* Wilcoxon signed rank test */
proc univariate data=tmax;
  var result;
  ods output Quantiles=quant;
  ods output TestsforLocation=pvalues(where=(test='Signed Rank'));
run;

/* Paired sample t-test */
proc ttest data=all;
  title "Paired sample t-test";
  paired Control * Treatment;
run;
```

In the example SAS code, this is currently presenting a lower-tailed test, however this may need adjusting for some of the comparisons.

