11. CHANGES FROM THE PROTOCOL SPECIFIED STATISTICAL ANALYSES

There were no changes from the protocol specified statistical analyses.

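### The SAP's rule for the primary Drug Liking Emax takes in the 0 h rating, although the protocol limits Emax to the 24 hours after dosing

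*SAP*

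**What the plan says.** - **Endpoint.** Protocol Section 4 (Table LAHB.1), like the synopsis, defines the primary endpoint through Emax "during the 24 hours after dosing of the at-the-moment 100-mm bipolar Drug Liking Visual Analog Scale (VAS) scores". Protocol 10.3.3 places the "hypothesis tests of primary interest at the peak of drug response effects", meaning Emax.
- **Derivation.** SAP 9.4.2 is the only place where Emax is computed. It takes the "maximum at-the-moment Drug Liking VAS score among all the individual values that are collected at the scheduled assessment timepoints". Time to Emax is the time point of that maximum. The rule covers both the Qualification Phase and the Treatment Phase.
- **Schedule.** Protocol 2.1 and 2.2 list the battery on Day 1 at "0, 0.25, 0.5, 1, 1.5, 2, 2.5, 3, 3.5, 4, 4.5, 5, 6, 8, 12" hours, and again at 24 h on Day 2. The only items limited to later times are given in the comment: "Overall Drug Liking and Take Drug Again assessed at 12 and 24 hours postdose only". At-the-moment Drug Liking is therefore rated at 0 h.
- **Precedence.** SAP Section 3 states: "This SAP supersedes the statistical considerations identified in the protocol; where considerations are substantially different, they will be so identified". SAP Section 11 states: "There were no changes from the protocol specified statistical analyses".

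**The concern.** The two documents define different variables. The protocol's Emax is the largest of 15 postdose ratings. The SAP's is the largest of 16 ratings, one of them at 0 h. A rating made before dosing cannot carry information about the treatment of that period.

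Adding it can only raise Emax, and it does so mainly in periods where liking stays low after dosing. Placebo is affected most and alprazolam hardly at all. The consequences for the three primary comparisons are:

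- **H1, alprazolam minus placebo (margin 15):** the difference shrinks. This costs a little power for the validation test and cannot produce a false validation.
- **H2, alprazolam minus lasmiditan (margin 5):** any rise in lasmiditan Emax shrinks the difference, which is conservative.
- **H3, lasmiditan minus placebo (margin 14):** either direction is possible. The difference falls slightly, making H3 easier to pass, if lasmiditan is liked more than placebo. It rises, making H3 harder, if some subjects dislike lasmiditan.

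Time to peak effect is also a reported result, and the literal rule allows it to be 0 h.

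**Working it through.** **1. Is 0 h predose?** Neither schedule labels the VAS 0 h point as predose, and the VAS window is ±15 minutes, so this is an inference. Three things support it:
- Protocol 5.1 says of Qualification Phase liking that "response will be assessed before and after alprazolam and placebo administration".
- Vital signs are also scheduled at 0 h on Day 1, and SAP 9.5.5 takes their baseline as Day 1 predose.
- SAP 9.3.1 sets predose PK sampling times to zero, and the Treatment Phase PK grid also starts at 0.

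**2. The plan's own power figure.** Inputs from Protocol 10.1 and SAP Section 7: SD of differences 16, about 50 completers, one-sided 0.05, assumed differences 22, 12 and 7, margins 15, 5 and 14.
- Distance to the margin: 22 − 15 = 7, 12 − 5 = 7, 14 − 7 = 7 mm.
- SE = 16/√50 = 2.263 mm.
- Normal approximation: Φ(7/2.263 − 1.645) = 92.6%.
- Noncentral t: 92.0% with 49 df. With the mixed model's residual df (250 − 1 − 49 − 4 − 4 = 192) it is 92.5%.

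The stated 90% or more is reproduced.

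**3. Size of the shift (inputs assumed).** The documents give no predose distribution, within-period rating SD or serial correlation. I assumed ratings around 50 that follow an AR(1) series over 0 h and the 15 postdose times, with 0 h as the first element (400,000 profiles per case). The rise in mean placebo Emax, in mm, was:

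| SD | corr. 0.5 | 0.7 | 0.8 | 0.9 | 0.95 |
|---|---|---|---|---|---|
| 2 mm | 0.068 | 0.073 | 0.073 | 0.067 | 0.055 |
| 3 mm | 0.104 | 0.108 | 0.110 | 0.101 | 0.083 |

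The 0 h rating was the maximum in 7.4 to 12.9% of placebo periods. With alprazolam at +22 mm at its peak, its Emax did not move (0.000 mm).

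**4. Effect on H1.** Power is the noncentral t with distance (7 − shift)/2.263:

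| Shift (mm) | 49 df | 192 df |
|---|---|---|
| 0 | 92.0% | 92.5% |
| 0.055 | 91.7% | 92.1% |
| 0.11 | 91.3% | 91.8% |

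Power falls to 90% at a shift of 0.285 mm (49 df) or 0.355 mm (192 df).

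**5. Effect on H3.** At a true difference of 14 mm, raising only placebo by 0.055 or 0.11 mm gives a type I error of 5.25% or 5.5% instead of 5%. Two lasmiditan profiles were tried, with the tmax (1 to 2.5 h) and half-life (4 to 6 h) from Protocol 3.2:
- All subjects 7 mm above placebo: lasmiditan minus placebo changes by −0.055 to −0.108 mm.
- Half at +22 mm and half at −20 mm: it changes by +0.356 to +0.903 mm, which is conservative for H3.

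**6. How far the assumptions matter.**
- The placebo shift scales with the rating SD: about 0.14–0.18 mm at SD 5 and 0.22–0.29 mm at SD 8.
- If every predose rating is exactly 50, the shift is at most 0.01 mm.
- If the 0 h rating is drawn independently of the postdose ratings, with predose SD 2 to 5 mm and within-profile noise 0.5 to 5 mm, placebo Emax rises by 0.00 to 1.44 mm. The top of that range needs predose ratings far more scattered than the placebo ratings that follow.
- An independent 0 h rating combined with a correlation of 0.95 between later ratings (SD 3 mm) gives 0.753 mm and H1 power of 86.0–86.6%. That combination is not coherent, since the 0 h rating would then be unrelated to one made 15 minutes later.

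**The case against.** The strongest reply is that the protocol already settles the window. The SAP supersedes only the protocol's statistical considerations, whereas the endpoint is defined in Protocol Section 4. The SAP itself expands Emax as the maximal effect score, and a rating made before dosing is not an effect. Together with the statement that nothing changed, this makes the protocol window the likely intention. That much stands. It does not repair the sentence: SAP 9.4.2 is a positive rule, it is the only derivation, and a programmer who follows it will include 0 h.

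A second reply is that the 0 h point is nowhere labelled predose for the VAS, and that the before-and-after wording concerns only the Qualification Phase. This is correct, and the reading remains an inference, though a well-supported one. If 0 h meant something else, the SAP would still need to say what.

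A third reply is that the simulated sizes come entirely from chosen inputs. This also stands:
- The range of 0.055 to 0.11 mm is an illustration and should not be read as an estimate.
- The like/dislike result depends on the curve shape. A one-compartment curve gives roughly +0.45 to +1.1 mm instead.
- The power comparison assumes that the design values of 22 and 16 refer to an Emax without the 0 h rating, which the documents do not say.

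Finally, the qualification criteria are not expressed as Emax, so no effect on the selection of subjects is shown.

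**Conclusion.** The concern holds, as a minor point. As written, the SAP's derivation differs from the protocol's primary endpoint, and the difference is not declared. Its practical effect is probably small. Under the linked-series assumptions with SD 2 to 3 mm, H1 power stays above the stated 90% and the type I error for H3 moves by at most half a percentage point. H1 cannot be falsely validated, and the effect on H2 is conservative. No figure in the documents bounds the size, and larger scatter in the 0 h ratings would make it larger. The conclusion rests on reading 0 h as predose, which is very likely but not stated.

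**What to change.** Add to SAP 9.4.2:

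> Emax and time to Emax use the postdose ratings only (0.25 to 24 h); the 0 h (predose) rating is excluded. This applies in both the Qualification Phase and the Treatment Phase.

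This restores the protocol's endpoint, rules out a time to Emax of 0 h, and makes the statement in SAP Section 11 true on this point. The cost is one sentence and one programming filter before unblinding. No new data are needed, and sample size, alpha, margins and the visit schedule are unchanged.

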7. SAMPLE SIZE JUSTIFICATION

The study design and analysis methods are as prescribed in “Assessment of Abuse Potential of Drugs: Guidance for Industry” published by the US Food and Drug Administration (FDA), January 2017 (FDA 2017)³. Three different hypothesis tests are of primary interest:

1. Validation test of the sensitivity and integrity of the study: Does the positive control (C) produce mean responses that show greater abuse potential compared to placebo (P)?

$$H1_0: \mu_C - \mu_P \leq \delta_1 \text{ versus } H1_a: \mu_C - \mu_P > \delta_1 \text{ where } \delta_1 > 0$$

2. Does the test drug (T) produce mean responses that show less abuse potential compared to positive control?

$$H2_0: \mu_C - \mu_T \leq \delta_2 \text{ versus } H2_a: \mu_C - \mu_T > \delta_2 \text{ where } \delta_2 \geq 0$$

3. Does the test drug produce mean responses that show similar abuse potential, compared to placebo?

$$H3_0: \mu_T - \mu_P \geq \delta_3 \text{ versus } H3_a: \mu_T - \mu_P < \delta_3 \text{ where } \delta_3 > 0$$

Approximately 60 subjects will be randomly assigned to 1 of 10 treatment sequences, in order to get approximately 50 completers. Subjects who are randomized but who do not complete all 5 periods during the Treatment Phase may be replaced. Replacement subjects will enter the same treatment sequence as the original subject to complete all 5 periods. Treatment sequence assignment will be determined by the repeated Williams square design, as shown in Figure 1.

This will lead to 90% or more power for testing each of the hypotheses of primary interest listed above, with the following assumptions:

- standard deviation of differences of 16 for the Drug Liking VAS (estimate based on within-subject standard deviation estimate of 11.4 from previous studies [Blanchard et al. 2010]⁴)
- actual mean difference between alprazolam and placebo of 22 or more for the Drug Liking VAS,
- actual mean difference between alprazolam and lasmiditan of 12 or more for the Drug Liking VAS,
- actual mean difference between lasmiditan and placebo of 7 or less for the Drug Liking VAS,
- $\delta_1 = 15$, $\delta_2 = 5$, and $\delta_3 = 14$; and
- one-sided significance level of 0.05.

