The residuals from the mixed-effect model will be investigated for normality using the Q-Q plot. If this normality assumption is not met, paired sample t-test or nonparametric test will be considered based on actual data distributions. For nonparametric analyses, pairwise treatment comparisons will be assessed using the Wilcoxon signed-rank test on the within-subject differences, and median and interquartile range will be reported.

Descriptive statistics for each other element of the Drug Effects VAS Battery, aside from the Drug Liking VAS, and for time to peak effect will be reported for each study phase and treatment. If the normality assumptions of mixed effects model on the residuals are met, a linear mixed-effects model similar to that employed for the E_{max} of Drug Liking VAS will be employed for each other element of the Drug Effects VAS Battery.

Descriptive statistics for each element of the Drug Similarity Visual Analog Scale Battery – Baseline and Drug Similarity Visual Analog Scale Battery will be reported for each study phase and treatment.

The pattern of missing data will be assessed in the population of patients who entered into the treatment phase and took at least 1 dose of study drug in the treatment phase by looking at the trend of dropout rates among the first 4 periods, as well as comparing the dropout rates among the 5 treatments.

A sensitivity analysis will be performed on all patients who entered into the treatment phase and received at least 1 dose of study drug in the treatment phase, regardless of completion of all the 5 periods. The same mixed model and model diagnosis procedure as the primary analysis will be implemented.

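### The example SAS code for the primary Emax tests leaves out the 15, 5 and 14 mm margins, so the line labelled as the one-sided test compares each difference with 0 mm

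*SAP*

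**What the plan says.** SAP 9.4.2 defines seven primary comparisons of Drug Liking Emax at one-sided 0.05:

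- H1, alprazolam minus placebo: null of at most 15 mm.
- H2, alprazolam minus each of the three lasmiditan doses: null of at most 5 mm.
- H3: "each dose of lasmiditan minus placebo, with the null hypothesis that the difference is ≥ 14 mm".

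The same margins stand in SAP section 7 and in Protocol 10.1 and 10.3.3. SAP section 3 says that substantial departures from the protocol will be identified, and section 11 reports none. Least-squares means with 90% confidence intervals are promised for every paired difference.

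The code follows, introduced by "An example of the SAS code that will be used is as follows". The line commented as the test is "lsmeans trtmnt / pdiff=controll alpha=0.05; /*Test at 0.05 significance 1-sided". The fallback paired t-test has "paired Control * Treatment" with no null value or side. The fallback signed-rank step starts with "proc univariate data=tmax" and analyses a variable called `result`, whose content is not described. One caveat follows: "In the example SAS code, this is currently presenting a lower-tailed test, however this may need adjusting for some of the comparisons".

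**The concern.** The text and the code specify different tests. `PDIFF=CONTROLL` on raw `emax` asks whether a treatment mean lies below the control mean, so its null is a difference of 0. None of 15, 5 or 14 appears anywhere in the code.

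The caveat points at the wrong item. With alprazolam as control for H1 and H2, and placebo as control for H3, the lower tail already suits all seven primary comparisons. The margin is what is missing, and no change of tail supplies it.

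At stake are the p-values labelled as the primary tests. They would be too lenient for H1 (the study-validity test) and H2, and almost impossible to pass for H3. They could also lead to the opposite conclusion from the 90% interval compared with its margin.

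**Working it through.** **Inputs.** From SAP section 7 (same in Protocol 10.1): SD of differences 16 mm, about 50 completers, one-sided 0.05, and assumed differences of 22 (H1), 12 (H2) and 7 mm (H3). Margins of 15, 5 and 14 mm are from SAP 9.4.2. The documents give no degrees of freedom, so I show two values: 49 (paired test) and 192 (mixed model: 250 observations − 1 − 49 subjects − 4 periods − 4 treatments). Results appear in that order. I take the usual SAS behaviour that the null is 0 when no test value is given; the documents do not describe it.

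**Standard error.** SE = 16/√50 = 2.263 mm.

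**The plan's own power.** Each assumed effect lies 7 mm from its margin (22 − 15, 12 − 5, 14 − 7), so the noncentrality is 7/2.263 = 3.09. Power is 92.0% / 92.5% by noncentral t, and 92.6% by the normal approximation, Φ(3.094 − 1.645). This reproduces the SAP's claim: "This will lead to 90% or more power for testing each of the hypotheses of primary interest listed above, with the following assumptions".

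**The same data tested against 0.** The noncentrality becomes (true difference)/2.263, with the tail set to suit each hypothesis.

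| Test | True difference | Rejects, margin test | Rejects, test against 0 |
|---|---|---|---|
| H1 | 22 mm (planned) | 92.0 / 92.5% | over 99.9% |
| H1 | 15 mm (boundary) | 5% | over 99.9% |
| H2 | 12 mm (planned) | 92.0 / 92.5% | 99.98 / 99.99% |
| H2 | 5 mm (boundary) | 5% | 70.3 / 71.1% |
| H3 | 7 mm (planned) | 92.0 / 92.5% | about 0.0001% |
| H3 | 0 mm (dose equals placebo) | about 100% | 5% |

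The stated power therefore describes the margin tests, not the code.

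**Where the two rules part.** At 192 df the critical distance is 1.653 × 2.263 = 3.74 mm. Observed differences that give opposite answers are:

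- alprazolam minus placebo: 3.7 to 18.7 mm (15 + 3.74);
- alprazolam minus lasmiditan: 3.7 to 8.7 mm (5 + 3.74);
- lasmiditan minus placebo: −3.7 to 10.3 mm (14 − 3.74).

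At the planned effects, the code's p-value and the 90% interval set against the margin disagree in 7.5-8% of trials for H1, 7.5-8% for H2 and 92% for H3.

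**Full design.** I simulated 20,000 trials with the ten sequences of the SAP's Figure 1, five completers each, and subject, period and treatment effects. At a true alprazolam-minus-dose difference of 5 mm, the code rejected in 71.1-71.7% and the interval rule in 4.9-5.2%. At a true dose-minus-placebo difference of 7 mm, the code never rejected and the interval rule did so in 92.3-92.6%.

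**Range of SD (assumed 12 to 20).** H2 at a true 5 mm, tested against 0, rejects 90% of the time at SD 12 and 54-55% at SD 20. H3 at a true 7 mm, tested against 0, never exceeds 0.003%, while its margin test goes from 99% to 79%.

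**Contrasts covered.** Five treatments give 5 × 4/2 = 10 paired differences. One `PDIFF=CONTROL` call gives 4. Two calls, with alprazolam and then placebo as control, give 4 + 4 − 1 = 7, which are the primary ones. The three dose-versus-dose intervals that the text promises are left out.

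**The case against.** The strongest reply is that the tests are already fully specified directly above the code, and that the code is plainly a skeleton: it has a placeholder dataset and names no control level, so it cannot be run unchanged. A 90% interval limit compared with the margin is exactly the one-sided 0.05 margin test, and those intervals are planned. Every error rate above assumes that a programmer overlooks the printed margins. The content of `result` is unknown, so a margin may already have been subtracted there. The table shells, which are not available here, may state the decision criteria.

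Much of this stands. The hypotheses, design and sample size are not in question, and the error rates are conditional. The p-value against 0 also agrees with the interval's relation to 0; the conflict is with the interval's relation to the margin. The signed-rank step may be correct once its input is known. The three dose-versus-dose intervals are not primary.

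It does not remove the mismatch. Nowhere does the SAP say that the tests are decided by comparing interval limits with the margins. The only output it labels as the test is the p-value against 0. Its own note on what may need changing names the tail and not the margin.

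**Conclusion.** The concern holds as a conflict between text and code on the primary test, and it should be fixed. The stated hypotheses are correct and agree with the power statement; the code labelled as the test does not implement them.

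The consequence arises only if the code is run without margins. Under the SAP's planning values the H2 boundary error would then be 70-71% and the H1 boundary error over 99.9%, each instead of 5%, and H3 power would fall from 92% to practically nil. These sizes rest on an SD of differences of 16, 50 completers, and the default SAS null of 0. Over an SD range of 12 to 20 the direction is the same and the errors remain large.

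**What to change.** Align the code in SAP 9.4.2 with its text in one of two ways.

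- **State the rule.** H1 is rejected if the lower 90% limit exceeds 15 mm, H2 if the lower 90% limit exceeds 5 mm, and H3 if the upper 90% limit is below 14 mm. Drop the test label from the `PDIFF=CONTROLL` line.
- **Code the tests.** Write seven contrasts with explicit values and sides: 15 upper; 5 upper for each dose; 14 lower for each dose. `LSMESTIMATE` with `TESTVALUE=` and `UPPER` or `LOWER` does this.

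In both cases, request all ten 90% intervals with `LSMEANS trtmnt / PDIFF=ALL CL ALPHA=0.1`.

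Carry margin and side into the fallback code: `H0=` and `SIDES=` in `PROC TTEST`, and `MU0=` with a one-sided p-value in `PROC UNIVARIATE`. The text says that "pairwise treatment comparisons will be assessed using the Wilcoxon signed-rank test on the within-subject differences", so name the within-subject Emax differences as the input to the signed-rank step in place of `tmax`.

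The cost is one sentence or a short code edit. Hypotheses, design, data collection and sample size stay as they are.
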